## **Protocol**

### **Study design**

This was a two phase feasibility study exploring appropriate management, setting, participants including inclusion and exclusion criteria, attrition rates, protocol, and retention. Outcome data for each stage were collected during baseline, acquisition, short-term, and long-term retention. The study was approved by the Institutional Review Board at both Western Carolina University, reference number 949671-4, and Mission Health Systems, reference number 1124795-3. Minimal exertion during the activity was the only potential harm for this study. All participants provided written informed consent prior to data collection. There were no outside funding sources.

### **Study Participants**

During Phase I, participants with history of a chronic stroke (>6 months) and ability to sit statically without physical assistance were eligible for the study. Individuals with severe hemineglect (star cancellation test <44/54) or inability to follow multistep commands were excluded. There were no issues with these criteria during the first phase, so the same criteria were used to recruit participants with acute stroke in an inpatient rehabilitation setting for Phase II. Unfortunately, some qualified participants were unable to complete the task so throughout the study exclusion criteria was modified to individuals with orthopedic issues that limited their ability to weight shift including severe hip or back pain, individuals with other neurologic conditions such as dementia, and individuals with contraversive pushing.

\* BodiTrak. Model BT1526-8578. Vista Medical Ltd [name]

† iPad. Apple Inc. [name]

‡ Body Align Pro. serial number 86300861. Motion Unlimited Corporation California. [name].

## **Investigators**

Although the principal investigators were both faculty members at Western Carolina University, one of which was a licensed physical therapist, the other investigators were student physical therapists. During Phase I, each investigator filled one of three roles during data collection for the entire phase: script reading, computer management, or patient guarding. Lack of cross-training created difficulty in data collection, therefore in Phase II investigators were trained for all roles. Different student groups conducted each phase of the feasibility study and were trained primarily by the previous student group. Inconsistencies with both instruction and data collection persisted suggesting changes in investigator training are necessary prior to a randomized controlled study.

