### **Randomization and blinding**

During Phase I, stratified randomization was used based on gender. Results from a 2013 study showed significant differences between gender during focus of attention trials suggesting the potential need for randomization based on gender. Group allocation was randomly selected for the first male and first female participants. Each following participant was alternately placed in either the internal or external focus of attention group. During Phase II, gender-based stratification was not used, to explore whether the intervention groups would naturally be comparable based on gender, age, BMI, and Function in Sitting Test scores. Instead, a blocked randomization with a random number generator (blocks of 10) was used to determine the order of focus group allocation. A blinded statistician and a graduate assistant performed the random number generation and placed the group assignments into separate envelopes, which were then sealed. Group assignment remained in sealed envelopes until after baseline measurements were completed. The participants and statistician were blinded for both phases of the feasibility study.

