### **Procedures**

\* BodiTrak. Model BT1526-8578. Vista Medical Ltd [name]

† iPad. Apple Inc. [name]

‡ Body Align Pro. serial number 86300861. Motion Unlimited Corporation California. [name].

During Phase I, individuals in both groups sat unsupported on a hi-lo mat table which was adjusted so participants were sitting at 90 degrees hip and knee flexion with feet shoulder width apart. Tape marks were used to mark initial set up ensuring standardized positioning for each trial. Following baseline trials, all participants watched the same instructional video describing lateral weight shifting. The instructions included correct mechanics that should be used when weight shifting laterally with focus on correct form needed for the movement.

Testing included baseline, acquisition, short term retention (5 minutes later), and long-term retention (7-10 days later). Participants performed three trials of seated weight shifting to each side at all timepoints. During acquisition, the internal focus group was instructed to “shift your weight as much as possible towards your right or left hip without using your arms”. The external focus group sat with targets one arm length away at shoulder height and were instructed to “shift your body weight as much as possible towards the blue/orange target without using your arms.” During baseline and retention trials, adults were instructed to “lean as far as you can to the right/left without using your arms.” During Phase II, the protocol was similar except 6 trials were performed for acquisition to potentially improve motor learning, which was not significant in Phase I per retention data. Other changes to the protocol included allowing participants to move their feet when weight-shifting. Instructions were also revised. The external focus group was told to “move your shoulder as close to the blue/orange target as possible”, while the internal focus group was told to “shift your body weight as much as possible towards your right/left hip without using your arms.” These instructions were too dissimilar and had

\* BodiTrak. Model BT1526-8578. Vista Medical Ltd [name]

† iPad. Apple Inc. [name]

‡ Body Align Pro. serial number 86300861. Motion Unlimited Corporation California. [name].

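### Prompts are read aloud by investigators who are not listed as blinded, and delivery is admitted to be inconsistent; recorded prompts would remove an avoidable source of noise and possible bias in an effort-dependent outcome

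*Combined protocol and SAP*

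**What the plan says.** **Who delivers the prompts.** The Investigators section says that, apart from two faculty principal investigators, "the other investigators were student physical therapists". In Phase I, "each investigator filled one of three roles during data collection for the entire phase: script reading, computer management, or patient guarding". This caused difficulty, and so "in Phase II investigators were trained for all roles". The section then reports the result: "Inconsistencies with both instruction and data collection persisted suggesting changes in investigator training are necessary prior to a randomized controlled study".

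**Who is masked, and until when.** Under Randomization and blinding, "The participants and statistician were blinded for both phases of the feasibility study". Investigators are not on that list. For Phase II the section adds: "Group assignment remained in sealed envelopes until after baseline measurements were completed".

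**What is said to participants.** Under Procedures, the acquisition cue differs by arm: the internal group is directed to a hip, the external group to a coloured target. Baseline and retention use one common prompt to lean as far as possible. Short-term retention follows 5 minutes after acquisition, and long-term retention 7 to 10 days after.

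**What is measured.** Under Outcome measures, a pressure mat records lateral excursion of the center of pressure in both phases. Phase II adds shoulder alignment from video.

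**The concern.** The intervention is a sentence spoken by an investigator, and the response is how far a person leans when asked for a maximum. Tone, repetition, pacing and encouragement can change that response directly, whatever the focus of attention. The plan says that instruction was not uniform and that the Phase II change to training did not cure this.

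Two consequences need to be kept apart. Inconsistency unrelated to arm widens the spread of excursion and makes a real focus effect harder to see. Inconsistency that follows the reader's knowledge of the arm would shift one group relative to the other and could be mistaken for a focus effect. The second matters most at retention, where both arms should hear the same neutral words and where learning is judged.

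The remedy the section names is a change in investigator training. That can reduce variation between readers, but it does not stop the reader from knowing the arm.

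**Working it through.** **Step 1: what the text establishes and what is inferred**

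| Point | Basis | Status |
|---|---|---|
| A person reads the prompts during the session | Script reading is a data-collection role (Investigators) | Close to explicit; the word live is not used |
| Instruction was inconsistent after Phase II cross-training | Investigators | Stated |
| The acquisition reader knows the arm | The cue wording identifies the arm (Procedures) | Follows necessarily |
| The retention reader knows the arm | Investigators are not listed as blinded, and no masked reader is described | Inferred; the reader at retention is not identified |
| Inconsistency differed by arm | Nothing in the documents | Not shown |

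**Step 2: whether existing safeguards reach the problem**

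- Scripted wording fixes the words, but not tone, repetition or added encouragement.
- The instructional video, the same for both arms, covers the mechanics of weight shifting. It does not carry the focus cue or the retention prompt.
- Participant blinding limits expectation in the participant, not in the reader.
- The pressure mat protects the measurement, but not the effort being measured.
- Sealed envelopes in Phase II protect baseline. Acquisition and both retention tests come later.

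No recorded cue, masked retention reader, check of delivery or adjustment for investigator is described.

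**Step 3: illustration of the bias route**

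The documents give no figure for the inconsistency and no alpha, SD or effect size, so there is no figure of theirs to reproduce. Assumptions: an equal split of the 26 Phase II participants (26 / 2 = 13 per arm), no true focus effect, a two-sided 5% two-sample t-test, and a delivery difference between arms of *d* SD.

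Degrees of freedom = 2n − 2. Noncentrality λ = d × √(n/2). False-positive rate = P(|T| > t_crit), where T is noncentral t with those degrees of freedom and noncentrality λ.

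For n = 13: df = 24, t_crit = 2.064, √(13/2) = 2.550.

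| d (assumed) | λ | False-positive rate |
|---|---|---|
| 0 | 0 | 5.0% |
| 0.2 | 0.510 | 7.8% |
| 0.4 | 1.020 | 16.5% |
| 0.5 | 1.275 | 23.2% |

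The Data analyses section reports high attrition at long-term retention but gives no count. To show the direction, take n = 6 per arm (also an equal split of the 12 in Phase I): df = 10, t_crit = 2.228, √(6/2) = 1.732. Then d = 0.2 gives λ = 0.346 and 6.1%; d = 0.5 gives λ = 0.866 and 12.3%. Fewer participants mean less inflation. By the same formula, a larger randomized study would make a fixed delivery difference more likely to reach significance.

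**The case against.** The strongest reply is that the document describes a feasibility study already carried out, discloses the instruction problem itself, and says training must change before a randomized trial. The wording was scripted, both arms saw one video, participants were blinded, and the outcome comes from an instrument. All of this is correct and lowers the risk. It does not close the gap, because none of it masks the reader or standardizes tone.

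A reader might infer more than the text supports, in three ways. First, that the same arm-aware team opened the envelopes, delivered the cue and then gave the retention prompt. The documents say when assignments stayed sealed, but not who opened them, who prompted at retention, or whether the same people returned 7 to 10 days later. Second, that the admitted inconsistency was biased by arm. The Investigators section reports inconsistency without linking it to arm or giving a direction, so by itself it supports added noise. Third, that the illustrated error rates estimate what happened. The shifts are assumed, and the t-test simplifies the planned 2 × 3 and 2 × 4 mixed ANOVAs. At 0.2 SD the inflation is modest.

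The documents separately concede that the Phase II cues were too dissimilar in content. That is a different fault: perfectly matched wording would still be read by someone who knows the arm.

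**Conclusion.** The point holds as a risk to be designed out, not as demonstrated bias. It is firm that investigators read the prompts, that delivery was inconsistent after cross-training, that investigators are not listed as blinded, and that the acquisition reader knows the arm. That the retention reader also knew the arm is a reasonable inference only.

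The certain cost is noise of unknown size. The possible cost is a biased contrast: under the assumptions in the working, a false-positive rate between about 8% and 23% for arm-linked differences of 0.2 to 0.5 SD at 13 per arm, and lower with the smaller numbers at long-term retention. These rates illustrate sensitivity and are not evidence that a difference of any given size occurred. The change is worth making because its main part is cheap and acts directly on a problem the plan itself reports.

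**What to change.** In the protocol carried forward to the randomized study:

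1. Deliver every baseline, acquisition and retention prompt as a fixed audio recording, played once per trial on equipment the study already has (the tablet or the computer). Allow no added verbal encouragement. Permit replay of the same recording when a participant misses a prompt. The cost is recording a few sentences; the downside is less freedom to repeat or rephrase.
2. Optionally, where cross-trained staffing allows, have the retention prompts run by a team member who was not present at acquisition, with any targets out of view. This cannot be called free: team size is not stated, short-term retention comes only 5 minutes after acquisition, and staff in the guarding and computer roles could still know the arm.
3. State in the blinding section who opens the assignment, who runs each test, and which of them know the arm. This costs a few sentences.

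Step 1 removes inconsistency in spoken delivery even if staff remain aware of the arm. Step 2 addresses that awareness at retention.

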## **Setting**

Phase I was conducted with individuals with a chronic stroke in two different outpatient clinics. Findings from this phase showed no significant differences between the focus of attention groups. These findings along with previous findings in the chronic stroke population in other studies suggest there may be more significant differences seen in those with acute stroke. Muckel and Merholz were able to show differences in performance in focus of attention in those with acute stroke during a similar weight shifting task. Based on these findings, Phase II was conducted in the inpatient rehabilitation setting.

## **Recruitment and retention**

Twelve adults with chronic stroke (mean age  $61.4 \pm 13.8$  years; 6 months to 13 years post-unilateral stroke) with good trunk control (Function in Sitting Test mean score  $51 \pm 2.9/56$ ) were recruited for Phase I. Recruitment of participants was primarily from

\* BodiTrak. Model BT1526-8578. Vista Medical Ltd [name]

† iPad. Apple Inc. [name]

‡ Body Align Pro. serial number 86300861. Motion Unlimited Corporation California. [name].

outpatient settings, local physical therapy clinics or physician offices, located in a rural area, thus the sample size was limited.

To allow for recruitment of a larger sample than in Phase I, Phase II was conducted in an inpatient setting. Participants were recruited via staff physical and occupational therapists at the facility. Twenty-six adults post-acute stroke (mean age  $61.8 \pm 17$ , 1-10 weeks post unilateral stroke), with good trunk control (Function in Sitting Test mean score  $51.3 \pm 4.4$  out of 56) were recruited.

### **Randomization and blinding**

During Phase I, stratified randomization was used based on gender. Results from a 2013 study showed significant differences between gender during focus of attention trials suggesting the potential need for randomization based on gender. Group allocation was randomly selected for the first male and first female participants. Each following participant was alternately placed in either the internal or external focus of attention group. During Phase II, gender-based stratification was not used, to explore whether the intervention groups would naturally be comparable based on gender, age, BMI, and Function in Sitting Test scores. Instead, a blocked randomization with a random number generator (blocks of 10) was used to determine the order of focus group allocation. A blinded statistician and a graduate assistant performed the random number generation and placed the group assignments into separate envelopes, which were then sealed. Group assignment remained in sealed envelopes until after baseline measurements were completed. The participants and statistician were blinded for both phases of the feasibility study.

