### **Data analyses**

To summarize participant characteristics, descriptive data included means and standard deviations for continuous variables and counts for categorical variables. Percentages were reported to specify whether recruitment and retention goals were met based on power analysis. For Phase I, a 2 (group) X 4 (time) repeated measures mixed model ANOVA was

\* BodiTrak. Model BT1526-8578. Vista Medical Ltd [name]

† iPad. Apple Inc. [name]

‡ Body Align Pro. serial number 86300861. Motion Unlimited Corporation California. [name].

used to examine the whether the demonstration, instructions, and set up differentiated between focus of attention groups at the different timepoints of the study. Phase II utilized both a 2 (group) X 3 (time) and 2 (group) X 4 (time) mixed model ANOVA to analyze the relationship of focus of attention on performance during the different timepoints. Data including long term retention trials were examined separately due to high attrition rates. If the sphericity assumption was violated, Huynh-Feldt (H-F) and Greenhouse Geisser (G-G) corrections were used to correct the degrees of freedom to report F values. When the overall model was significant, the post hoc pairwise comparison was used, with a Bonferroni correction, to examine differences between every two timepoints in each group. Adverse events would be counted as any falls or health issues requiring medical attention such as a cardiac event.

\* BodiTrak. Model BT1526-8578. Vista Medical Ltd [name]

† iPad. Apple Inc. [name]

‡ Body Align Pro. serial number 86300861. Motion Unlimited Corporation California. [name].

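### Phase I allocation was stratified by gender, but its ANOVA has no gender term; if gender is prognostic, the between-group test is conservative and loses power

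*Combined protocol and SAP*

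**What the plan says.** Randomization and blinding states "During Phase I, stratified randomization was used based on gender". The reason given is an earlier study that "showed significant differences between gender during focus of attention trials suggesting the potential need for randomization based on gender". The first man and the first woman were allocated at random, and then "Each following participant was alternately placed in either the internal or external focus of attention group".

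Data analyses gives the model: "For Phase I, a 2 (group) X 4 (time) repeated measures mixed model ANOVA was" the method used. For Phase II it names 2 x 3 and 2 x 4 group-by-time models. Gender is neither a factor nor a covariate in any of them.

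For Phase II, Randomization and blinding says "gender-based stratification was not used, to explore whether the intervention groups would naturally be comparable". The characteristics to be compared are gender, age, BMI and sitting function. The same section adds that "a blocked randomization with a random number generator (blocks of 10) was used to determine the order of focus group allocation". Participant characteristics are to be summarised descriptively. The document sets no criterion for comparability and no rule for handling an imbalance.

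**The concern.** Stratifying on a factor takes its effect out of the contrast between groups. If the factor is then left out of the model, its variance stays in the between-participant error. The reported standard error exceeds the true one, so the test rejects too rarely under the null and has less power under the alternative. This bears on a result that was used: Setting cites the absence of significant group differences in Phase I, together with other studies, as grounds for moving Phase II to acute stroke.

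The Phase II issue is separate and smaller. Under valid randomisation, balance in a single allocation is a chance result. Its distribution follows from the sample size and the allocation method and can be calculated beforehand. Seeing balance once therefore gives little guidance on whether the later randomised study should stratify.

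**Working it through.** The plan has no figure to reproduce. Data analyses mentions a power analysis but gives no alpha, effect size, power or target sample size.

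**Inputs from the document.** Phase I has 12 participants ("Twelve adults with chronic stroke") and Phase II has 26 (Recruitment and retention). The models and allocation methods are as set out above.

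**Assumptions, because the document gives no values.** Phase I has 6 men and 6 women, alternated within gender, so 3 of each per group. Alpha is 0.05 two-sided. Gender effects *s* run from 0 to 1.5 SD. Group effects *d* are 1.8 SD (chosen to put power near 80%) and 1.0 SD. The SD is that of a participant's averaged outcome within group and gender.

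**Step 1: Phase I error term.** With gender coded 0/1 and split 6/6, its sum of squares about the mean is 12 x 0.25 = 3. Gender is orthogonal to group, so all of 3*s*² falls into the residual, which has 12 - 2 = 10 df. The expected residual mean square is therefore 1 + 3*s*²/10 times the true variance, and the standard error is too wide by roughly the square root of that.

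**Step 2: Phase I between-group test, by simulation, gender omitted.**

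| Gender effect (SD) | SE factor | Type I error | Power, d = 1.8 | Power, d = 1.0 |
|---|---|---|---|---|
| 0 | √1.000 = 1.00 | 5% | 80% | 35% |
| 0.5 | √1.075 = 1.04 | about 4.5% | 78-79% | 32% |
| 1.0 | √1.300 = 1.14 | 3% | 71% | 25% |
| 1.5 | √1.675 = 1.29 | 1.5% | 60% | 17% |

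With gender in the model, type I error is about 5% and power about 79% (d = 1.8) or 34% (d = 1.0) in every row.

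**Step 3: group x time interaction.** If gender adds a constant γ to a person's outcome at every timepoint, then outcome(t) - outcome(baseline) contains γ - γ = 0. A simulation with four timepoints, within-person correlation 0.7 and an equal gender split (all assumed) agrees. For gender effects of 0, 1 and 1.5 SD, the interaction type I error is 4.9%, 5.1% and 4.9% in Phase I and 5.0%, 4.9% and 5.0% in Phase II. Power for a 0.5 SD post-baseline effect stays at 16-17% in Phase I and 35-36% in Phase II. Only a gender difference in the time course would disturb this test.

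**Step 4: Phase II between-group test.** Allocation was not stratified, so omitting gender leaves type I error near 5%. With 13 per arm and 13 of each gender assumed, and d = 1.0, power without gender is 68%, 65% and 58% for gender effects of 0, 0.5 and 1 SD. With gender in the model it is about 66%.

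**Step 5: chance gender imbalance in Phase II.** Assume 13 per arm and *M* men among 26, and let *x* be the number of men in one arm, which is hypergeometric. The arms differ by 4 or more men when |2*x* - *M*| ≥ 4.
- *M* = 8 (x ≤ 2 or x ≥ 6): 2 x (0.0008 + 0.0143 + 0.0857) = 20%.
- *M* = 10 (x ≤ 3 or x ≥ 7): 2 x (0.0001 + 0.0017 + 0.0189 + 0.0924) = 23%.
- *M* = 13 (x ≤ 4 or x ≥ 9): 2 x (0.0006 + 0.0079 + 0.0492) = 12%. Here the difference is always odd, so 4 or more means 5 or more.

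Twenty-six is two full blocks of 10 plus 6 of a third. If each block holds five per arm, the arms are 13/13 with probability 0.476. Allowing for the other splits, the chance that the arms differ by at least 20 percentage points in gender is 31-34% for 8 to 13 women. A difference of 4 men shifts the unadjusted between-group contrast by 4/13 = 0.31 SD if the gender effect is 1 SD. By Step 3, a constant gender effect contributes nothing to the interaction.

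**The case against.** The strongest reply is that the test of interest is the group x time interaction. Baseline precedes the focus instructions, so the question of whether focus changes performance over time is a within-person one. Step 3 supports this. A reader might infer that the whole Phase I analysis is conservative, but the documents support that only for the between-group effect.

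A reader might also infer that the Phase I standard errors are too wide outright. That needs a real gender effect, and the document supplies none. It cites one earlier study as suggesting a potential need. At 0.5 SD the loss is small, and at zero the extra term costs a little power.

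It can also be said that a gender main effect does not capture gender modifying the response to focus. That is correct. A gender x time term covers a different time course by gender. Modelling a different focus effect by gender would need group x gender terms, which 12 participants cannot support.

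Finally, a reader might infer that the investigators used Phase II balance to decide against stratification. The text says only that they wished to explore comparability. It reports no conclusion and no decision. Unstratified blocked randomisation is valid in itself, and varying the allocation method between feasibility phases is legitimate.

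**Conclusion.** The mismatch between the Phase I design and its model is real, and its effect is conditional. If gender is prognostic, the Phase I between-group test is conservative: negligibly so at 0.5 SD, with power 71% against 79% at 1 SD and 60% against 79% at 1.5 SD (d = 1.8, 6 men and 6 women assumed). Type I error is never inflated. The interaction is untouched unless gender changes the time course. Nor does the omission by itself explain the Phase I null result: at d = 1.0, power is at most about 35% with or without gender.

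The Phase II point is secondary. The stated aim of exploring natural comparability cannot be met by one allocation of 26, but the document claims no answer. It is enough to treat the observed balance as a description of this sample.

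**What to change.** - **Phase I:** add gender as a between-participant factor, with its gender x time term. The cost is 1 between-participant df (10 to 9) and (2 - 1) x (4 - 1) = 3 df for gender x time (within-participant error 30 to 27). If gender has no effect, about 1 point of power is lost (80% to 79% at d = 1.8).
- **Phase II:** name gender as a prespecified covariate in both models. If gender has no effect, the cost is about 2 points (68% to 66% at d = 1.0). The document is written in the past tense, so where results have already been seen, present the adjusted analysis as a labelled sensitivity analysis.
- **Comparability:** state that Phase II balance on gender, age, BMI and Function in Sitting Test is descriptive only. Base any stratification in the later randomised study on how strongly each factor predicts outcome and on imbalance risk calculated for the planned sample size and method.

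Gender was needed for the Phase I allocation and the Phase II comparison, so no new data are required. The change is one factor in the model and a sentence or two of text.
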